Q-actin is an imino-sugar (idoBR1, (2R,3R,4R,5S)-3,4,5-trihydroxypiperidine-2-carboxylic acid) isolated from fruits of certain cucumbers, *Cucumis sativus* (Cucurbitaceae). The daily dose will be 20mg, which will be divided into two vegan gummies (2x10mg) that are to be consumed before bed. The placebo is a gummy matching Q-actin in appearance, taste and texture, the ingredients for which are detailed in section 4.

3.2) Quality

Q-actin (and the matching placebo) will be consumed in the form of wax coated, square bottom gummies that are dark red in colour with natural raspberry flavouring. Vegan gummies were chosen as opposed to tablets because they are easier to consume than pills/capsules. Both Q-actin and the placebo have been manufactured by a fully licensed GMP site manufacturer. The gummies have been analysed and quality control screened for elemental elements and microbials and have passed, all according to guidelines..

3.3) Dose

The dose of Q-actin and the placebo will be 2x10mg gummies daily before bed, for a period of 12 weeks.

4) Investigational Product Safety

The Food Standards Agency have confirmed that Q-actin, can be used in clinical trials. A food grade statement for Q-actin has been obtained, and a GRAS document (Generally Recognised As Safe) status has been prepared for the producers in America (Gateway Health Alliances, Inc./IminoTech, Inc.) by Soni & Associates Inc. Gummy ingredients: Corn Syrup, Sugar, Purified Water, Pectin, Natural Flavours (raspberry), Citric Acid, MCT Oil, Natural Colors (vegetable concentrates), Carnauba Wax, Sodium Citrate

5) Study Design

5.1) Objectives of the Study

The aim is to compare physical strength, finger dexterity, hip and knee pain, quality of life, sleep quality, diet, and urine chemical composition between baseline and post intervention after Q-actin and placebo control.

5.2) Subject Selection

- 50 participants, over 50 years, mixed gender, mixed ethnicity
- Inclusion Criteria:
 - Consenting adults >50 y Age.
 - Commit to urine sampling.
 - Able to commit to attending WARU or the remote centre for measurements of physical strength, finger dexterity, quality of life, sleep quality, hip and knee pain, and diet choices.
 - Able to restrict from consumption of cucumber, gherkins, and melon for two days before coming to WARU or the remote centre.
- Exclusion Criteria:
 - Showing (or anyone within the household) any COVID-19 symptoms (see COVID-19 basic health screen).*
 - Higher risk or vulnerable from coronavirus or live with someone at a higher risk of a severe illness from COVID-19 (over 70, undergoing cancer treatment, high risk of getting infections).
 - Had a letter from the NHS advising you to shield (isolate).
 - Had been at risk of exposure to COVID-19 such as travel, contact with someone with COVID-19, been exposed to the virus, or has been asked to self-isolate by the track and trace system.
 - Serious health conditions that require daily long-term medication.
- *If the potential participant has had COVID-19 previously (and are fully recovered and not within isolation) then they are eligible to join the study

GDPR: For the data the Welsh Government requires, Welsh Government is the data controller and Aberystwyth University (WARU) is the data processor. For any other data, including sensitive personal data, the data controller and the data processor is Aberystwyth University (WARU).

5.2) Study Design

This is a randomised, double-blinded, parallel study, where participants are asked to take the gummies (Q-actin or Placebo) twice a day for a period of 12 weeks. Within that 12 week period, participants will be required to make three visits to the Well-being and Health Assessment Research Unit (WARU) at Aberystwyth University, or to the remote facility in Trimsaran, following a pre-induction screening visit. Urine kits and study materials will be prepared (and stored) at the Well-Being and Health Assessment Research Unit (WARU) at Aberystwyth University. Urine samples will be assessed at AberInnovation and Aberystwyth University.

Pre-Induction

Participants are welcomed with tea or coffee and talked through how safe working practices are being conducted during coronavirus (COVID-19). Then they are introduced to the urine sampling boxes and provided with crib sheets and an email link to a video demonstration (if needed). They are talked through the logistics of study visits and the tasks that will be completed. They are asked to complete a medical health screening questionnaire, and height, weight, and BMI measurements are obtained. They are provided with the urine sampling kits complete with 1 needle, two sampling vacutainers and 1 collection cup for each visit (week 0, week 6 and week 12). A review of their continued right to withdraw, in addition to the data protection and storage of their personal data and biofluids, is provided, and the dates and times of visits 1, 2 and 3 are arranged. A consent form is signed. This pre-induction can also be done remotely and materials posted. Consent forms are to be received and stored prior to the first sample collection.

Visit 1

Participants arrive on their pre-organised day and time with 2 x 4ml of their first urine sample (after being stored between 3-5 degrees Celsius in participants home fridge), collected at home using our urine kits. Consent is obtained followed by the first assessment of physical strength, finger dexterity, quality of life (EQ-5D), sleep quality (PSQI), diet (PDQS) and hip and knee pain (WOMAC). They collect their gummies for the full 12-week period. The gummies are divided into 12 packets (labelled with the participants unique, pseudonymised code), with each packet consisting of 14 gummies (for 2 gummies x 7 days). On the first visit they will receive 6 packs (for the first 6 week, and on the second visit they will receive the remaining 6 packs)

Visit 2

On their pre-organized day and time, participants repeat the activities undertaken during visit 1. Second assessment of physical strength, finger dexterity, quality of life, sleep quality, diet choices, hip and knee pain, and week 6 urine drop off. On the second visit they will receive the remaining 6 packs of supplements.

Visit 3

On their pre-organized day and time, participants repeat the same activities as undertaken during visits 1 and 2. Final assessment of physical strength, finger dexterity, quality of life, sleep quality, diet choices hip and knee pain and week 12 urine drop off.

6) Participant Risks

The supplements have been tested for any adverse effects, so no risks are anticipated. However, participants are informed that if any negative effects occur, then they should refrain from continuing in the study and to inform the research team. The urine kits contain a needle, so care should be taken.

7) Benefits to participant

There is no financial incentive for participants if they decide to join this study. They will be allowing the researchers gain important insight into the anti-inflammatory properties of the cucumber supplement and the digestion and metabolism of the supplement within urine. This will be the first time this type of research will have been conducted and will be a valuable pilot study before the researchers can investigate further human health benefits in the future.

8) Ethical approval

Aberystwyth University Research Ethics Panel confirmed a favourable ethical opinion subject on the 27th October 2022.

9) Privacy/confidentiality

Participants are informed that only the researchers involved with the study will be able to look at the information they provide. Specific details and personal identifiers will only be available to the researchers. At the end of the study, any information relating to participants will be made pseudonymous (coded without their name associated). Participants will not be identifiable in any publication that may arise from this research. Electronic files will be kept in a logical manner and will always be kept grouped within specific folders and password protected, and backed up. There may be times when keeping paper forms are necessary (consent forms), but in this case the paper versions will be kept in a locked filing cabinet. All biofluids are stored in a locked freezer. Key is kept by the gatekeeper.

This research is being conducted in accordance with the GDPR guidelines. The AU Data Protection Manager provides oversight of AU activities involving the processing of UK GDPR and special category data, and can be contacted at [contact]. Personal data will be stored securely and processed for metabolomic analysis. The legal basis that would be used to process personal data will be 'a task in the public interest'. If participants are concerned about how personal data is being processed, AU can be contacted in the first instance at [contact]. If they remain dissatisfied, they may wish to contact the Information Commissioner's Office (ICO). Contact details, and details of data subject rights, are available on the ICO website at: <https://ico.org.uk/for-organisations/data-protection-reform/overview-of-the-gdpr/individuals-rights/>.

10) Safety Monitoring

Participant:

If a participant, or a member of their family/household become unwell during the study, then they are pre-warned to alert a member of the research team immediately using the contact information they

GDPR: For the data the Welsh Government requires, Welsh Government is the data controller and Aberystwyth University (WARU) is the data processor. For any other data, including sensitive personal data, the data controller and the data processor is Aberystwyth University (WARU).

have been provided. Participation in the study will be suspended immediately until further discussion with the research team has taken place. If they become unwell at any point and need medical assistance, they are advised to contact 111 and seek advice from the NHS health sector or their doctor's surgery. We have a duty of care towards them and can help monitor their health remotely over 14 days and will help in any way we can.

Data:

See Privacy/confidentiality

In exceptional circumstances, confidentiality may have to be breached in cases where persons are considered to be at risk or if required by law.

11) Data analysis and statistics

The chemical composition of urine samples will be assessed at AberInnovation and Aberystwyth University using high resolution metabolomics. Self-report data will be analysed in WARU using appropriate methods.

12) Sponsors and contacts

Welsh Government is the sponsor. Gateway Health Alliances, Inc and Phytoquest are the companies. Main contact is [name], Aberystwyth University [contact]

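### Does the undated COVID-19 exposure exclusion shut out the recovered volunteers whom the footnote admits?

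*Protocol*

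**What the plan says.** Protocol section 5.2 (Subject Selection) plans for "50 participants, over 50 years, mixed gender, mixed ethnicity" and then lists the exclusions. Four of the five concern COVID-19, and three of those matter here, along with the footnote.

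- **Symptoms:** "Showing (or anyone within the household) any COVID-19 symptoms (see COVID-19 basic health screen". This entry carries the asterisk that leads to the footnote.
- **Higher risk:** "Higher risk or vulnerable from coronavirus or live with someone at a higher risk of a severe illness from COVID-19 (over 70", with further examples after it.
- **Exposure:** "Had been at risk of exposure to COVID-19 such as travel, contact with someone with COVID-19, been exposed to the virus", continuing "or has been asked to self-isolate by the track and trace system". No period before screening or before a visit is given, and there is no asterisk.
- **Footnote, after the last exclusion:** "If the potential participant has had COVID-19 previously (and are fully recovered and not within isolation) then they are eligible to join the study".

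No other part of the protocol gives a look-back period for exposure or an order of precedence between the exposure entry and the footnote. The basic health screen is cited only at the symptom entry, and its content is not in the document. Section 8 dates the ethics opinion: the panel "confirmed a favourable ethical opinion subject on the 27th October 2022".

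**The concern.** Infection implies exposure. If the exposure entry covers a volunteer's whole past, everyone admitted by the footnote is excluded by that entry, and one list gives opposite answers for the same person. The layout does not settle it, because the asterisk ties the exception to symptoms and not to exposure.

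Letting the footnote prevail settles only part of it. A recovered volunteer would be eligible. A volunteer who once travelled or had a contact, and was never infected, would stay excluded without limit.

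At stake would be who is enrolled, whether 50 participants can be found, and how the pilot's population is described. Assessments take place at WARU or at a remote facility, and pre-induction may be done remotely, so an unstated window could also lead to different decisions on similar volunteers.

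**Working it through.** The protocol has no figure on this point to reproduce. The check is a reading of the passages against one another, a look at whether the effect can be sized, and a look at what could reach the results.

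**1. Is the overlap real on the literal text?** Yes. Under an unlimited exposure rule, those infected and recovered are a subset of those ever exposed, so the footnote's group lies wholly inside the excluded group.

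**2. Is the unlimited reading the natural one?** The surrounding text points the other way.

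| Place | Wording or content | Time frame it implies |
|---|---|---|
| Exclusions, symptom entry | "Showing (or anyone within the household) any COVID-19 symptoms (see COVID-19 basic health screen" | Present |
| Exclusions, exposure entry, last clause | "or has been asked to self-isolate by the track and trace system" | A tracing instruction, which concerns a current risk of transmission |
| Footnote | "If the potential participant has had COVID-19 previously (and are fully recovered and not within isolation) then they are eligible to join the study" | Separates past infection from present isolation |
| Section 10, Safety Monitoring | Illness in a participant or household suspends participation pending discussion, with remote monitoring offered over 14 days | Temporary |

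The exposure entry also names travel as an example of risk. With no time limit, that would remove almost every volunteer and leave the footnote with nobody to admit. A reading that empties another sentence of the same list is unlikely to be the one intended. The reading that gives both sentences work to do is that exposure means current or recent exposure, and that a past, resolved infection is no bar.

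**3. Can the effect on recruitment be sized?** Only by assumption. Among volunteers who meet every other criterion, let the shares be *a* never exposed, *b* exposed but never infected, and *c* infected and recovered. Volunteers needed to enrol 50 = 50 / eligible share, rounded up.

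| Assumed a / b / c | Unlimited exposure rule: 50/a | Footnote prevails: 50/(a + c) | Only current exposure counts, none current: 50/1 |
|---|---|---|---|
| 40 / 30 / 30% | 50/0.40 = 125 | 50/0.70 = 71.4, so 72 | 50 |
| 20 / 30 / 50% | 50/0.20 = 250 | 50/0.70 = 71.4, so 72 | 50 |
| 10 / 60 / 30% | 50/0.10 = 500 | 50/0.40 = 125 | 50 |

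The arithmetic is right, but none of the shares comes from the document. The first column applies only if staff use the reading that step 2 finds implausible. The last column assumes that nobody is currently exposed. The table shows that a literal rule would be costly. It does not show that this trial faces that cost.

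**4. Could the ambiguity reach the treatment comparison?** Eligibility acts on who enters. Section 5.2 (Study Design) describes a randomised, double-blinded, parallel trial. If eligibility is decided without knowledge of the allocation, both arms are drawn from the same screened group under any reading, and in expectation they hold the same mix of exposed, recovered and never-exposed people. Looser or stricter screening at one location changes the composition of the whole sample but does not favour an arm.

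**5. Does the upper age matter?** The entry that names those over 70 combines with the inclusion of those over 50 to give an effective range of over 50 to 70. An exclusion that narrows an inclusion is how such lists ordinarily work. The limit is stated where it applies, so there is no inconsistency.

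**The case for a change.** The strongest case for a change is that eligibility rules belong in the protocol and should not need interpretation. The list uses the present tense where it means the present, and the exposure entry is in the past tense. The protocol also sets an explicit window elsewhere, two days for avoiding cucumber, gherkins and melon, so the authors could have set one here. A reader who infers recent exposure must still choose how recent, and two screeners may choose differently. The ethics opinion dates from late October 2022 and the footnote itself anticipates previously infected volunteers, so the case will arise. The remedy would be a sentence or two.

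Most of the textual part stands: there is no window, the asterisk is on one entry only, and letting the footnote prevail still leaves the exposed-but-never-infected group formally undated. It does not stand that staff cannot apply the list. A specific exception that ends in plain eligibility would ordinarily override a general exclusion, and the gap is filled by reading exposure as current or recent. The unseen health screen cuts both ways: it cannot be shown to cover exposure, and staff cannot be shown to lack a working window. Different choices between screeners would slightly blur the description of the sample without altering a result.

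**Conclusion.** The exposure entry is loosely worded and the footnote's reach is not marked on it, but this is missing detail that those running the screening would fill sensibly. No change to the plan is called for.

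The effect on the treatment comparison is nil, on the assumption that eligibility is settled before the allocation is known. No endpoint, analysis or figure in the protocol depends on the entry. The effect on recruitment cannot be estimated from the document, and the large volunteer counts in the table arise only under invented shares combined with an implausible reading. What is left is a small loss of precision in saying whom the pilot describes. The length of any window and the reach of the footnote are for the sponsor and investigators to state.

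The conclusion rests on the inferred intent that exposure means current or recent exposure and that the footnote is an exception to it. A recruitment log showing recovered volunteers turned away for past exposure would contradict that inference. Even then the damage would be to recruitment and to the description of the sample, not to the comparison between arms.

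### Section 6 ties any negative effect to leaving the study, so week-6 and week-12 outcomes can be lost, and it is not reconciled with Section 10

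*Protocol*

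**What the plan says.** - **Protocol, Section 6 (Participant Risks).** Participants are told that "if any negative effects occur, then they should refrain from continuing in the study and to inform the research team". The instruction concerns the study, not only the gummies, and has no threshold of severity. The same paragraph says the supplements have been tested, "so no risks are anticipated".
- **Protocol, Section 10 (Safety Monitoring).** The trigger is "If a participant, or a member of their family/household become unwell during the study". The consequence is: "Participation in the study will be suspended immediately until further discussion with the research team has taken place". Remote health monitoring over 14 days is offered; outcome visits are not mentioned.
- **Protocol, Section 5.2 (Study Design), Visits 2 and 3.** All post-baseline outcomes are collected at these two visits. Visit 2 is the "Second assessment of physical strength, finger dexterity, quality of life, sleep quality, diet choices, hip and knee pain, and week 6 urine drop off". Visit 3 is the "Final assessment of physical strength, finger dexterity, quality of life, sleep quality, diet choices hip and knee pain and week 12 urine drop off".
- **Protocol, Section 5.1 (Objectives).** The outcomes are to be compared "between baseline and post intervention after Q-actin and placebo control".

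**The concern.** Stopping a product and leaving a trial are different events. The first is a matter of treatment; the second ends data collection. Section 6 merges them: a participant who follows it after any negative effect has no reason to attend the remaining visits, and the protocol has no other route by which the outcomes would be obtained.

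Whether someone has a negative effect can depend on what they were given. Loss of this kind may differ between arms, or remove different sorts of people from each arm, and a comparison of those who stay is then no longer protected by randomisation. Even without bias, each lost visit costs precision in a trial of 50.

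The overlap with Section 10 adds doubt about what staff and participants should do. For someone unwell on the gummies, one section reads as leaving and the other as a pause pending discussion. Neither says whether assessments continue.

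**Working it through.** **The text, side by side**

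| Question | Section 6 | Section 10 |
|---|---|---|
| Trigger | Any negative effect | Participant or household member unwell |
| Consequence | Not continuing in the study; tell the team | Participation suspended until discussed with the team |
| Is this leaving or a pause? | Reads as leaving | Reads as a pause; resumption not described |
| Do Visits 2 and 3 still take place? | Not stated | Not stated |
| Reference to the other section | None | None |

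The triggers overlap for a participant who becomes unwell on the gummies. Household illness falls under Section 10 only.

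**Size: an illustration**

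The protocol gives a total of 50 participants. It gives no allocation ratio, SD, target difference, error rate, power or dropout rate, so there is no figure to reproduce. Assumed here: 25 per arm, SD 1, a two-sided 5% test, and leavers whose outcomes would have been worse than stayers' by a gap of 0.5 or 1.0 SD, the same gap in both arms. The target is the mean over everyone randomised.

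*Bias.* If a fraction p of an arm leaves, the stayers' mean is better than the whole arm's mean by p × gap. The completer comparison is therefore biased by (p in one arm − p in the other) × gap, in favour of the arm with more leavers.

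*Standard error.* SE = √(1/n₁ + 1/n₂), with n₁ and n₂ the numbers remaining. With all 50, SE = √(2/25) = 0.283.

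*Error rate.* With b = bias/SE, the actual two-sided rate is P(Z > 1.96 − b) + P(Z < −1.96 − b).

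- **2 versus 1 leavers.** Difference in fractions 2/25 − 1/25 = 0.04. Bias 0.04 × 0.5 = 0.02 or 0.04 × 1.0 = 0.04 SD. SE = √(1/23 + 1/24) = 0.292, up 3.2%. b = 0.07 or 0.14. Error rate 5.05% or 5.2%.
- **5 versus 1 leavers (20% versus 4%).** Difference in fractions 0.16. Bias 0.08 or 0.16 SD. SE = √(1/20 + 1/24) = 0.303, up 7.0%. b = 0.26 or 0.53. Error rate 5.8% or 8.3%.
- **5 versus 5 leavers.** Difference in fractions 0, so bias 0. SE = √(2/20) = 0.316, up 11.8%.

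*Precision.* Difference detectable with 80% power (two-sided 5% t-test, noncentral t):

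| Remaining per arm | Detectable difference (SD) |
|---|---|
| 25 and 25 | 0.81 |
| 23 and 24 | 0.84 |
| 20 and 24 | 0.87 |
| 20 and 20 | 0.91 |

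These are chosen inputs, not bounds.

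**The case against.** **The sentence is lay safety advice.** It sits under participant risks and may be loose wording for stopping the gummies and telling the team. The visit dates are arranged at pre-induction and are not made conditional on taking the product. The participant information pages are not available to this review, so what participants are told about follow-up may be clearer. This is fair as to intent. It does not remove the problem: the text says the study, someone who has left the study does not attend, and nothing elsewhere corrects that reading.

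**Sections 6 and 10 can be read as one sequence: stop, inform, discuss.** The triggers also differ in part. This stands to the extent that the two sections do not contradict each other in every case. What remains is an unreconciled overlap for a participant unwell on the gummies.

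**The harm is hypothetical and small in the milder case.** This also stands. Every rate and gap above is assumed, the 8.3% needs 20% versus 4% leaving together with a 1.0 SD gap, and the protocol anticipates no risks.

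**The bias calculation presumes that off-product outcomes belong to the target.** The protocol fixes no estimand and describes an exploratory pilot. That is correct. For the interest in "the digestion and metabolism of the supplement within urine" (Section 7), off-product samples would not help. But if visits end with the product, the wording has settled the choice in advance: a comparison of everyone randomised can no longer be made from observed data, whichever target the analysis later adopts.

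**Conclusion.** The concern holds as a point about wording and design that should be corrected. Section 6, followed as written, ends outcome collection for a participant with any negative effect, and it is not reconciled with Section 10. This is a rule the protocol states, not a detail left to an analysis plan.

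Bias is possible but not shown. Under the assumptions above it is negligible if very few leave (at most 0.14 of a standard error with 2 versus 1). It reaches about half a standard error if a fifth of one arm leaves, 4% of the other leaves, and leavers are 1.0 SD worse. Equal leaving with equal gaps gives no bias but still costs precision. If nobody has a negative effect, nothing is lost. Confidence is medium, because the intended meaning of the sentence and the rate of negative effects are both unknown.

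**What to change.** 1. Reconcile Sections 6 and 10 so that a participant unwell on the gummies falls under one consistent statement.
2. Word stopping the product, suspension of participation and withdrawal of consent as three separate events.
3. State that participants who stop or interrupt the product are still invited to the week-6 and week-12 assessments already scheduled, unless they withdraw consent or the team's safety discussion concludes that they should not attend.
4. Record the date and reason for each interruption, and whether each outcome, urine included, was collected on or off product.

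Whether and when the product is stopped is a clinical matter for the sponsor and the investigator and is not addressed here.

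**Cost.** Changes to protocol and information-sheet wording, one on/off-product field per visit and some follow-up effort. No assessment and no participant is added. The downside is that a few outcomes will be measured off product. Off-product urine does not inform metabolism of the supplement, so it must be flagged and kept apart for that question.
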